### 6.6. Interim Analyses

Interim analyses will be performed to support regulatory activities and publications. These analyses will be descriptive in nature and will not involve any formal hypothesis testing.

For an interim analysis, as this study will be ongoing, a cut-off approach will be implemented to ensure data quality. The interim analysis will include data entered on or prior to a pre-specified cutoff date. For assessments with starting/end dates (e.g., Exposure, AEs, medical history, medications), the starting date will be compared to the pre-specified cut-off date.

#### 7. STATISTICAL METHODOLOGY

### 7.1. Patient Disposition

Patient disposition will be summarized and include the total number and percentage of patients in the following categories:

- Enrolled Patients (signed informed consent and met eligibility)
- Treated Patients
- Completed Patients
- Safety Analysis Set
- PD Analysis Set
- PK Analysis Set

Summaries of the number and percentage who discontinued study treatment based upon primary reason for discontinuation (e.g. AE, Death, Lost to Follow-up, Physician Decision, etc.) will be presented. Summaries of the number and percentage who withdrew from study prematurely based upon primary reason for withdrawal (e.g. AE, Death, Lost to Follow-up, Physician Decision, etc.) will also be presented. Per patient data listings will be presented displaying the primary reason the patient discontinued treatment and/or went off study.

#### 7.2. Protocol Deviations

Protocol violations will be classified into major or minor deviation by medical review. A major deviation is defined as a deviation that may significantly impact the completeness, accuracy and/or reliability of the trial data; that may significantly affect a patient's rights, safety and well-being (ICH.E3 R1 Structure and Contents of Clinical Study Reports Guidance for Industry. 2013). Deviations not classified as major will be assigned as minor. All protocol deviations will be presented in a listing.

### 7.3. Baseline Characteristics

Baseline characteristics will be based upon the derived baseline in the parent study ALN-AS1-001 (Refer to ALN-AS1-001 SAP; dated 29 September 2017). These characteristics include but are not limited to age, sex, race, ethnicity, body weight, height, and body mass index (BMI) as well as genotype, prior hemin prophylaxis status, baseline ALA, PBG, and 5-aminolevulinic acid synthase 1 (ALAS1) levels.

Data recorded in medical history in this study and data recorded in the medical history of the parent study ALN-AS1-001 will be summarized by Medical Dictionary for Regulatory Activities (MedDRA) system organ class (SOC), high level term (HLT) and preferred term (PT). A patient only contributes once to the count for a given condition (overall, by SOC, by HLT, by preferred term). Medical history and pregnancy test results will also be presented in data listings.

### 7.4. Safety Analyses

The primary objective of this study is to evaluate the long-term safety and tolerability of givosiran in patients with AIP. All analyses will use the Safety Analysis Set. All clinical safety

laboratory data collected from the central laboratory will be used to evaluate safety. For summaries of ECG data, these will be performed separately based upon data collected locally and centrally.

**Parameters:** Safety and tolerability assessments for givosiran will include study drug exposure, AEs, clinical laboratory parameters (hematology, serum chemistry, liver function test [LFT], urinalysis, coagulation), vital signs, 12-lead ECGs, concomitant medication, and physical examinations.

**Exposure:** Summaries will include descriptive statistics of the duration of treatment (days) and total number of doses received. Additional summaries of the cumulative number of patients (percentage) that completed study treatment intervals (e.g.  $\ge 1$  day,  $\ge 1$  month,  $\ge 3$  month, etc.) and the number of patients (percentage) that completed study treatment at the latest visit interval will also be displayed. Additionally, cumulative number of doses received at home will be displayed.

The date of the last exposure to study drug is defined as the earliest day of the following dates:

- Last dose date + 27 days
- Analysis cut-off date
- The date of EOS

Duration of exposure (days) is defined as date of the last exposure – date of the first dose +1. Dose interruptions and compliance will not be considered when calculating of duration of exposure.

A separate per-patient exposure listing will be generated to display the dosing regimen in the parent study (ALN-AS1-001) and actual dosing (mg/kg) regimen(s) in this study.

**Adverse Events:** AEs will be coded using the MedDRA coding system (version 21.0 or later) and displayed in tables and data listing by SOC and PT. Patients who report multiple occurrences of the same PT will be classified according to the most related or most severe category. Patients with a missing severity or missing relationship to study drug will be classified to the most related or most severe category.

Summaries of AEs will consist of events which occur or worsen (including date/time when applicable) after the first dose of givosiran in this study. Note: Porphyria attacks are recorded on the AE eCRF, however they will not be reported as AEs but rather as an endpoint of clinical activity (see section 7.5.2); therefore, the term "AE" excludes porphyria events.

An overview of the frequency (percentage) of AEs including the total number of events will be tabulated (summaries such as but not limited to, the number of patients with at least 1 AE, the number of patients with at least 1 AE related to study drug, the number of patients with at least 1 serious AE [SAE], the number of patients who discontinued study drug to an AE). Separate tabulations will be generated by SOC and PT for all AEs, AEs by maximum severity, related AEs, related AEs by maximum severity, SAEs, discontinuation from study drug due to AEs, interruption due to AEs, and deaths. Patient listings will be generated separately for any patient who died, discontinued from study drug and reported any SAEs.

An additional set of AE outputs will also be generated by study groups defined by the initial dose of givosiran [i.e. Patients with an initial dose of 2.5 mg/kg (monthly) in ALN-AS1-002 and Patients with an initial dose of 5 mg/kg (at any time) in ALN-AS1-002].

#### **Adverse Events of Clinical Interest (AECIs):**

**Injection Site Reactions [ISRs]**: AEs mapping to the HLT="Injection Site Reactions" using MedDRA dictionary will be included in the summary. An ISR may consist of one or more signs or symptoms. Key summaries such as but not limited to will be generated: Number of patients with at least 1 ISR, percent of injections complicated by ISRs, frequency (percentages) of ISRs by PT (corresponds to individual sign or symptom). A separate listing will be generated to display all patients who reported ISRs.

**Hepatic AEs, including LFT abnormalities considered clinically significant by the investigator**: AEs mapping to the Standardized MedDRA Query (SMQ) Drug-related hepatic disorders - comprehensive search (includes all narrow and broad terms). The following key summaries will be generated: Frequency (percentages) of Hepatic SMQ Events by SOC and PT. A separate listing will be generated to display all patients who reported hepatic AEs.

**Acute pancreatitis:** AEs mapping to Acute Pancreatitis SMQ (narrow terms) plus the following PT terms (lipase increased, lipase abnormal, amylase increased, amylase abnormal, hyperlipasemia, hypermylasaemia, pancreatic enzyme abnormality, pancreatic enzymes abnormal, pancreatic enzymes increased). The following key summaries will be generated: Frequency (percentages) of Acute Pancreatitis Events by SOC and PT. A separate listing will be generated to display all patients who reported acute pancreatitis.

**Anaphylactic Reaction:** AEs mapping to the anaphylactic reaction SMQ. The following key summaries will be generated: Frequency (percentages) of anaphylactic reaction by search category (narrow and broad) and PT. A separate listing will be generated to display AEs that meet SMQ criteria.

#### **Other Adverse Events:**

**Malignancies:** AEs mapping to Malignant or Unspecified Tumors SMQ. The following key summaries will be generated: Frequency (percentages) of Malignancies by HLT and PT.

**Acute Renal Failure:** AEs mapping to the acute renal failure SMQ. The following key summaries will be generated: Frequency (percentages) of acute renal failure by SOC and PT.

Clinical Laboratory Parameters: Clinical laboratory parameters will be expressed in SI units. Laboratory data collected and recorded as below the LLOQ will be set to the lower limit of detection for calculation of summary statistics. Summaries generally include data from central laboratory. Certain summaries include data from both central and local laboratory (e.g., LFT).

Summary data for each laboratory parameter (hematology, serum chemistry, LFT, and coagulation), which are continuous variables, will have a tabular summary of descriptive statistics (n, mean, SD, median, quartiles, minimum, and maximum; see Appendix 2 for list of laboratory parameters). Descriptive statistics of actual value, change from baseline and percentage change from baseline at each scheduled visit will be displayed.

For each continuous parameter, severity will be categorized based upon Common Terminology Criteria for Adverse Events (CTCAE) version 4.03. Shift tables will be generated to summarize shifts from baseline category to the worst post-baseline category. Worst post-baseline category

will be considered the highest CTCAE grade or highest shift in ULN category unless otherwise specified (e.g. estimated glomerular filtration rate [eGFR]).

For hematology and chemistry laboratories, summary tables of potentially clinically significant abnormalities will also be provided.

The lipase and amylase (when applicable) will be categorized into the following categories:  $\leq$ ULN, >ULN and  $\leq$ 1.5xULN, >1.5xULN and  $\leq$ 2xULN, >2xULN and  $\leq$ 5xULN, >5xULN. A tabular summary will be generated to summarize the number and associated percentage of patient in each of the categories at any post-baseline visit. A by-patient listing of lipase values will be generated.

The eGFR (mL/min/1.73 m²) will be categorized into the following categories: ≥90,60-89, 45-59, 30-44, 15-29 and <15. A shift table of baseline to worst post-eGFR (i.e. category with the lowest value) will be presented.

All laboratory data will be presented in data listings, with potentially clinically significant values flagged. Out of range laboratory results will be identified in listings.

**Liver Function Tests (LFTs):** A listing will be generated for all patients with abnormal liver function tests as defined by ALT>3xULN, AST>3xULN or total bilirubin >2x ULN at any visit.

A tabular summary will be generated to summarize the number and associated percentage of patient in each of the categories at any post-baseline visit, shift tables will be presented for ALT, AST, total bilirubin:

- 1<ALT≤3, 3<ALT≤5, >5<ALT≤10, <10<ALT≤20, ALT>20xULN
- 1<AST\(\leq 3\), 3<AST\(\leq 5\), >5<AST\(\leq 10\), <10<AST\(\leq 20\), AST\(\leq 20\) XULN
- 1<ALT or AST≤3, 3<ALT or AST≤5, >5<ALT or AST≤10, <10<ALT or AST≤20, AST or ALT>20xULN
- ALP>1.5xULN
- 1.5<Total Bilirubin ≤2, 2<Total Bilirubin≤3, 3<Total Bilirubin≤5 and Total Bilirubin>5
- ALT or AST > 3xULN and Concurrent Total Bilirubin > 2xULN
- ALT or AST > 3xULN and Concurrent Total Bilirubin > 1.5xULN

Evaluation of drug-induced serious hepatotoxicity (eDISH) plots of peak bilirubin at any time versus peak ALT or AST at any time will also be presented. Spaghetti plots for patients who had worst ALT > 3xULN or total bilirubin > 2xULN will be presented (include data from both central and local laboratory).

**Vital Signs and Physical Examination:** Descriptive statistics for each vital sign (weight, height, oral body temperature, blood pressure, heart rate, and respiration rate) will be summarized at scheduled visits. In addition, a tabular summary of potentially clinically significant post-baseline abnormalities in vital signs will be presented. Per patient listing of vital signs results will be generated.

**ECG:** Summaries of ECG data will be generated separately for data collected locally and centrally. Note that baseline ECG data is only available based on local collection.

ECG findings will include rhythm, ventricular rate, PR interval, QRS duration, QT interval, corrected QT (QTc) interval. For each visit, the results will be the mean of the measurement from the triplicate ECG values for each patient at a single visit.

Descriptive statistics will be summarized at each scheduled visit. Change from baseline to each post-baseline assessment will be summarized (local ECG only). The number and percentage of patients with normal, abnormal or clinical significant abnormal results at each visit will also be summarized.

An outlier analysis will be performed for QTc using Bazett's (QTcB) and Fridericia's (QTcF) formula.

For local ECGs, categorical analysis via a shift table will be summarized as:

- The number and percentage of patients with maximum increase from baseline in QTcB/QTcF ( $\leq$ 30,  $\geq$ 30-60,  $\geq$ 60 milliseconds [ms]).
- The number and percentage of patients with maximum post-baseline QTcB/QTcF (≤450, >450-480, >480-500, >500 ms)

For central ECGs, categorical analysis will be summarized as follows:

• The number and percentage of patients with maximum post-baseline QTcB/ QTcF (≤450, >450-480, >480-500, >500 ms)

A per-patient listing of all ECG data will be generated for local and central data collection. A separate per patient listing with any post-baseline QTc value of > 500 ms or any patient with an increase from baseline of > 60 ms will also be generated.

**Prior and Concomitant Medications**: Concomitant medications will be coded using the WHO Drug Dictionary (March 2015 or later). Concomitant medications will be defined as any medication taken after the first dose of study drug in this study and any medication that started prior to the first dose in this study and was ongoing on or after the date of the first dose of study drug. If the end date of medication is missing or incomplete such that it cannot be determined whether it was prior to the first dose of study drug, it will be identified as concomitant.

Concomitant medications will be tabulated by Anatomic Therapeutic Class (ATC) and Preferred Term and by overall decreasing frequency of patients who took the medications. A patient listing will be provided for all prior and concomitant medications.

### 7.5. Secondary Analyses

#### 7.5.1. Pharmacodynamic Biomarkers

One of the key secondary objectives is to evaluate the long-term PD effect of ALN-AS1 on urine levels of ALA and PBG.

**ALA and PBG:** Analysis of ALA and PBG concentrations will be performed on the PD Analysis Set. Values will be based upon urine concentrations collected from the central laboratory. In all analyses of urine ALA and PBG, the concentrations will be expressed as mmol/mol of urine creatinine (e.g, creatinine normalized values). Any values recorded as <LLOQ will be assigned a value of LLOQ/2.

Data will be summarized descriptively (n, mean, SD, SEM, median, quartiles, minimum, and maximum) at baseline and each post-baseline scheduled visits. The analysis will be performed separately for scheduled assessments collected not during attacks and all scheduled timepoints. Tabular summaries of actual value, change from baseline and knockdown values (knockdown=-1\*percentage change) will be generated at each scheduled visit. Plots of the group means (±SEM) of actual values and knockdown values will also be generated. Per-patient plots of actual values over time will be generated.

### 7.5.2. Clinical Activity

Clinical activity of ALN-AS1 will be assessed by the number of porphyria attacks and by the number of doses of hemin administered.

Analysis of Clinical Activity will be performed on the Safety Analysis Set.

**Porphyria attacks:** An attack will be defined as any event with preferred term="Porphyria" recorded on Adverse Event eCRF. Attacks which occur within the same date (i.e., end date of attack is the same date as start date of the next attack) will be counted as one attack. When collapsing attacks that occurred on the same date, the following rules will be applied for severity and location:

- 1. Severity will be assigned the maximum severity among the records.
- 2. Location will be assigned 'hospital' if  $\geq 1$  attack with location=hospital. Location will be assigned 'outpatient' if  $\geq 1$  attack with location=outpatient Location will be assigned 'home' if all the records state location=home. Location will be assigned 'other' if all the records state location=other.

The number of porphyria attacks during the treatment period (attacks with start dates on or after date of first dose) will be summarized. Annualized attack rate (AAR) per patient will be calculated as the total number of porphyria attacks divided by the total person-days at risk and multiplied by the total number of days in a year (365.25). Person-days at risk will be defined as: (date patient went off study – date of first dose+1). For an interim snapshot, the person-days will be defined by date of the first dose until the minimum of the date of the interim snapshot cut-off date or date the patient went off study. For calculation of AAR, only records with non-missing start and stop dates will be considered.

Porphyria attacks will be summarized separately in each subgroup:

- 1. Composite attacks: Attacks requiring hospitalization, urgent health care (i.e. outpatient clinic, Emergency Department, etc.) or IV hematin at home.
- 2. Attacks requiring hospitalization
- 3. Attacks requiring urgent health care (i.e. Outpatient)
- 4. Attacks required treatment with IV hematin at home
- 5. Attacks not treated with IV hematin at home
- 6. All attacks

For each subgroup, the total number of events, total person-years (total days/365.25), mean rate (total number of events/total person-years) and SEM will be presented for each study group. The

SEM will be calculated using Cochran's estimate of SEM for weighted mean [1]. Attacks for each subgroup will display the rates separately for each phase of study: run-in (ALN-AS1-001 study) and treatment phase (ALN-AS1-002). A tabular summary of percentage change (%) in AAR rate from run-in to treatment phase will be also calculated per cohort. In addition, a by-patient listing will summarize the porphyria attacks in each of the subgroups. An exploratory analysis of AAR based on 6 months of givosiran dosing and beyond 6 months may be explored.

In addition, clinical activity will be assessed by duration and severity of attack (mild/moderate/severe). Reduction from run-in period (ALN-AS1-001 study) in composite to all attacks ratios will be assessed.

Hemin: Dosing with hemin will be summarized for doses during the treatment period (hemin start dates on or after the first dose of givosiran in this study). Hemin dosing will be identified as medication with standardized medication terms such as 'hematin', 'haem arginate' or 'hemin'. Annualized rate of hemin dosing will be summarized in the same manner as porphyria attacks (i.e., mean rate, SEM, person-years, total events). For the calculation of annualized rate of hemin, only records with non-missing start and stop dates will be considered. These summaries will also be presented in the same manner (i.e. separately for each cohort displaying results from each phase of study: run-in (ALN-AS1-001 study) and treatment phase (ALN-AS1-002). An exploratory analysis of Annualized rate of hemin dosing based on 6 months of givosiran dosing and beyond 6 months may be explored.

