#### 5. MISSING DATA

For continuous and categorical variables, data will not be imputed unless otherwise specified.

There will be no imputation used for partial and/or completely missing dates for events defined as 'porphyria attacks' and for dates of hemin medication. For Delta-aminolevulinic acid (ALA)/ Porphobilinogen (PBG) biomarkers, if any value is recorded as <Lower Limit of Quantification (LLOQ) then the assigned value used for calculations will be assigned a value of LLOQ/2.

The following rules will be applied to incomplete dates to determine the reporting of adverse events (AEs) or medications. These imputed dates will not be displayed in listings because these dates are used to determine if the medication was prior or concomitant to first dose in this study and if the AE occurred on or after the first dose in this study. The rules below do not apply to hemin medications or AEs defined as 'porphyria attacks'.

Imputation rules for Start Date of AE:

- If start date is completely missing, then start date will be imputed to be the date of the first dose of study drug
- For a partial start date (day is missing, month is missing or both day and month are missing):
  - partial date < the first dose date: the first day/month
  - partial date = the first dose date: the first dose date
  - partial date > the first dose date: the first day/month

For medications with partial start or stop dates: the first day/month will be imputed for start date, and the last day/month will be imputed for stop date.

For medications with a completely missing start date, the medications will be considered as started prior to the first dose of study drug in this study; medications will be classified as prior or concomitant depending on the medication stop dates. If any medications have a completely missing stop date, then the medication will be assumed as ongoing.

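### The annualized attack and hemin rates drop records without a stop date but keep their person-time, so the rates can only be unchanged or too low

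*SAP*

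**What the plan says.** All of the following is in the SAP. The rule is the same in all three versions in the file.

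- **Attack count (7.5.2).** Membership of the treatment period depends on the start date alone: "The number of porphyria attacks during the treatment period (attacks with start dates on or after date of first dose) will be summarized".
- **AAR numerator (7.5.2).** A second condition applies to the rate: "For calculation of AAR, only records with non-missing start and stop dates will be considered".
- **AAR denominator (7.5.2).** "Person-days at risk will be defined as: (date patient went off study" minus the first-dose date, plus 1. At an interim the end point is the earlier of the cut-off and the off-study date. Nothing is deducted for a dropped record.
- **Missing dates (section 5).** "There will be no imputation used for partial and/or completely missing dates for events defined as 'porphyria attacks". Hemin dates are treated the same way, and the rules for other AEs and medications are stated not to apply to either.
- **Interim cut-off (6.6).** The analysis takes data entered by the cut-off. For items with start and end dates, including AEs, "the starting date will be compared to the pre-specified cut-off date". Section 7.4 says attacks are recorded on the AE form.
- **Merging (7.5.2).** Records count as one attack when the "end date of attack is the same date as start date of the next attack".
- **Hemin (7.5.2).** "For the calculation of annualized rate of hemin, only records with non-missing start and stop dates will be considered".
- **Uses of the rate (7.5.2).** The percentage change in AAR from run-in to treatment is tabulated. There is also an optional split: "An exploratory analysis of AAR based on 6 months of givosiran dosing and beyond 6 months may be explored".

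**The concern.** Counting an attack needs only its start date. The stop date is needed for duration and for testing whether the next record continues the same attack. Requiring it for the rate removes events known to have happened and leaves their follow-up in place.

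At an interim this follows from the rules themselves and does not depend on poor data. Section 6.6 admits an ongoing attack by its start date, and section 7.5.2 then removes it because it has no stop date. Run-in attacks have had time to close by then, so the loss falls on the treatment phase and the change from run-in looks slightly better than it is. In the optional 6-month split, attacks open at a cut-off after month 6 fall almost entirely in the later part and flatter it. The attack count and the AAR can also disagree for the same patient.

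The rule is out of line with the rest of the SAP. Section 5 treats other medications with no stop date as ongoing, and section 7.4 assigns AEs with missing severity or relationship to the worst category. Attacks and hemin, the two measures of clinical activity, are the ones dropped, and dropping them favours the drug.

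**Working it through.** The SAP states no expected rate or attack duration, so there is no planned figure to reproduce.

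**Inputs.** From the SAP: up to 16 patients and up to 36 months of treatment (section 2); AAR = attacks / person-days x 365.25 (section 7.5.2). Assumed: all 16 patients followed to the stated time, a constant 3 attacks per patient-year, a mean attack duration *d* of 4, 7 or 10 days, and every attack in progress at the cut-off lacking a stop date. The cut-off times are also assumed, since the SAP gives none.

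**Direction.** The denominator does not depend on the record. A record without a stop date adds one attack, or none if it starts on the previous attack's end date, so dropping it lowers the count by one or leaves it unchanged. In 300,000 simulated patients with some stop dates missing, dropping records gave a lower count in 147,264, an equal count in 152,736 and a higher count in none.

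**Share of attacks lost.** With a constant rate, attacks open at the end of follow-up *T* are those begun in about the last *d* days. The expected share lost is *d*/*T*.

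| Follow-up | *T* (days) | Expected attacks (16 x 3 x years) | *d* = 4 | *d* = 7 | *d* = 10 |
|---|---|---|---|---|---|
| 6 months | 182.6 | 24 | 2.19% | 3.83% | 5.48% |
| 12 months | 365.25 | 48 | 1.10% | 1.92% | 2.74% |
| 36 months | 1095.75 | 144 | 0.37% | 0.64% | 0.91% |

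Simulation with exponential durations, for means of 4 and 10 days, gave 2.15% and 5.52% at 6 months, and 0.36% and 0.91% at 36 months. Widening *d* to 3-14 days gives 1.6-7.7% at 6 months and 0.27-1.3% at 36 months.

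**Number open at a cut-off.** 16 x 3 x *d*/365.25 = 0.53, 0.92 and 1.31 attacks. The chance of at least one is 1 - exp(-0.53) = 41% up to 1 - exp(-1.31) = 73%.

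**Change from run-in, with run-in records complete.** Apparent reduction = 1 - (1 - true) x (1 - loss).

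- 6 months, true 50%: 1 - 0.5 x 0.9781 = 51.1%, up to 1 - 0.5 x 0.9452 = 52.7%.
- 6 months, true 80%: 80.4% to 81.1%.
- 36 months: 50.2-50.5% and 80.1-80.2%.

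**Beyond-6-months window.** *T* becomes the cut-off minus 6 months. The loss is 4.4-11.0% with a 9-month cut-off, 2.2-5.5% at 12 months and 0.4-1.1% at 36 months.

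**One patient.** A single attack, open at 6 months: 1/182.625 x 365.25 = 2.0 per year if counted, 0 under the rule.

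**Hemin.** If each infusion is its own closed record, the effect is near zero. If one open record covers a course, it could be large. The SAP does not say which, so no figure is given.

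**The case against.** **Later stop dates might be kept.** Section 6.6 tests the start date and does not say that a stop date after the cut-off is blanked. If later stop dates were retained, only attacks unresolved at data extraction would be lost, and the interim figures above would be upper limits. But the same section admits only data entered by the cut-off, and the stop date of an ongoing attack cannot have been entered by then.

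**The restriction may be confined to per-patient rates.** The sentence closes the paragraph on the per-patient AAR, and the group rate is defined separately as events over person-years. However, the run-in comparison is itself described in terms of the AAR, so the natural reading carries the rule into the group summary.

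**The final effect is small.** This stands. It is under 1% of the rate at 36 months, and follow-up to month 39 or 42 would make it smaller. The 28-day limit after the last dose for patients who discontinue (section 6.5) also takes out some late attacks, but it does not remove the error. The summaries are descriptive and the endpoint is secondary. The largest figure, 4.4-11.0%, belongs to an assumed 9-month cut-off and an optional analysis.

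**The stop date serves merging.** This also stands in part. A missing stop date inside a chain of touching records can break the merging and push the count above the truth. That comes from the lost date: dropping the record still never counts more than keeping it. For a patient's last, still-open attack, counting by start date is plainly better. For gaps in mid-study, some under-counting may be exchanged for over-counting.

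**Hemin is unquantified.** Agreed. Section 7.5.2 names doses as the measure, which points to the dose as the unit, but the record structure is not stated.

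**Conclusion.** The concern holds. The stop-date condition takes known attacks out of the AAR numerator and leaves the denominator untouched, so compared with counting every recorded attack the rate is equal or lower.

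The pooled effect is modest at an early interim and minor at 36 months. Individual AARs, and a short later window in the 6-month split, are the most exposed. The sizes rest on the assumed rate, durations and cut-off times; the direction of the AAR error does not.

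The favourable shift in percentage change applies to an interim, where run-in records are closed. Away from an interim cut-off its direction depends on how complete the records are in each phase, which the SAP does not state. For hemin, the rule is the same and the size is unknown. No analysis that keeps open records is planned. This should be corrected, since the interim analyses are intended for regulatory use and publication.

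**What to change.** In section 7.5.2:

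1. Count in the AAR every attack whose start date is on or after first dose and on or before the cut-off, whether or not a stop date is known.
2. Require the stop date only for attack duration and for the same-date merging test. Treat a record without a stop date as a separate attack unless it starts on the previous attack's end date.
3. For hemin, count each recorded dose given on or after first dose whether or not the record has a stop date, and state whether one record is one dose or a course.
4. Report the number of attack and hemin records with missing stop dates, separately for run-in and treatment.

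The cost is a few sentences of SAP text, minor programming and one count by phase. The rates will be slightly less favourable, and a few records that cannot be tested for merging may be counted separately; the count in item 4 shows how many records could be affected.
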